Study Name: Palmitoylethanolamide and polydatin effect on pain and dysmenorrhea in women scheduled for laparoscopic treatment of possible endometriosis: a double blind randomised controlled trial

Protocol Number: 1 Version 0.5, dated 29 September 2020

Title:	Palmitoylethanolamide and polydatin effect on pain and dysmenorrhea in women scheduled for laparoscopic treatment of possible endometriosis: a double blind randomised controlled trial
Short Title:	The efficacy of Palmitoylethanolamide and polydatin on endometriosis pain study
Design:	Prospective double blind randomized controlled trial
Study Centres:	Gynaecology Unit 2, The Royal Women's Hospital Endosurgery Units A & B, The Mercy Hospital for Women Private practices in Parkville, Box Hill, East Melbourne, Brighton East, Fitzroy, Fitzroy North and Richmond
Hospital:	The Royal Women's Hospital, Parkville, Victoria Mercy Hospital for Women, Heidelberg, Victoria Epworth Hospitals, East Melbourne & Richmond, Victoria Frances Perry House, Parkville, Victoria Cabrini Malvern, Victoria Holmesglen Private, Victoria St Vincent's Private Hospital, Victoria Sunshine Hospital Warringal Hospital Sandringham Hospital
Study Question:	Can treatment by palmitoylethanolamide/ polydatin effectively reduce endometriosis related pain and what are the cellular and molecular mechanisms modified by PEA/PLD treatment in endometriotic lesions?
Primary Objectives:	
 1. To compare the change in dysmenorrhoea VAS score between PEA/PLD and placebo treatment in patients with endometriosis prior to laparoscopic surgical treatment. 2. To compare the change in dyspareunia, dyschezia and persistent pelvic pain VAS score between PEA/PLD and placebo treatment in patients with endometriosis prior to laparoscopic surgical treatment.

Study Name: Palmitoylethanolamide and polydatin effect on pain and dysmenorrhea in women scheduled for laparoscopic treatment of possible endometriosis: a double blind randomised controlled trial

Protocol Number: 1 Version 0.5, dated 29 September 2020

Secondary Objectives	
 1. To compare the change in dysmenorrhoea VAS score between PEA/PLD and placebo treatment at baseline and 4 months after laparoscopic surgery for endometriosis. 2. To compare the change in dyspareunia, dyschezia and persistent pelvic pain VAS score between PEA/PLD and placebo treatment at baseline and 4 months after laparoscopic surgery for endometriosis. 3. To compare the change in dysmenorrhoea, dyspareunia, dyschezia and persistent pelvic pain VAS score between PEA/PLD and placebo, before surgery, in patients without surgical evidence of endometriosis. 4. To compare the change in dysmenorrhoea , dyspareunia, dyschezia and persistent pelvic pain VAS score between PEA/PLD and placebo, before surgery, and 4 months after laparoscopic surgery without evidence of endometriosis. 5. To compare the change of quality of life between PEA/PLD and placebo treatment in women with surgical evidence of endometriosis, before and after surgery. 6. To compare changes in cellular and molecular markers from endometriotic lesions, blood and peritoneal fluid samples between patients treated by PEA/PLD and placebo. 7. To correlate changes in VAS score with changes in cellular and molecular markers, in patients with endometriosis, treated by PEA/PLD and placebo. 8. To assess the side effects of PEA/PLD.
Inclusion Criteria:	
 • Women aged 18 - 45 with pelvic pain scheduled for laparoscopic treatment of possible endometriosis. Both women with and without previous evidence of endometriosis on ultrasound or previous surgery are eligible. • Women who agree to use any type of contraception and avoid conceiving during the 8-week treatment phase. • English speakers
Exclusion Criteria:	
 • Pregnancy or actively trying to conceive • Breastfeeding • Previous hysterectomy • Suspected malignancy • Inability to provide informed consent
Number of Planned Subjects:	130 patients in each arm, 260 in total
Investigational product:	palmitoylethanolamide/ polydatin 400 mg/40 mg
S a f e t y considerations:	Worldwide, more than 800,000 patients have been treated with PEA for various chronic pain conditions. No serious side effects have been reported (36)

Study Name: Palmitoylethanolamide and polydatin effect on pain and dysmenorrhea in women scheduled for laparoscopic treatment of possible endometriosis: a double blind randomised controlled trial

Protocol Number: 1 Version 0.5, dated 29 September 2020

Statistical Methods:	
Continuous variables will be summarised as means with standard deviation if normally distributed or median with interquartile range if not. Comparisons will be performed using t-tests and Mann Whitney U tests respectively.
 
Categorical variables will be summarised as proportions and comparisons performed using Chi-squared and Fisher exact tests. P values of <0.05 will be considered significant.
 
The impact of the PEA treatment on continuous outcome pain measures will be assessed using linear modelling adjusting for the effect of covariates including pre-treatment pain measures.

Subgroups:	
 • Patients treated by palmitoylethanolamide/ • polydatin 400 mg/40 mg • Patients treated by placebo • Patients with surgically proven endometriosis • Patients with surgically proven absence of endometriosis

Study Name: Palmitoylethanolamide and polydatin effect on pain and dysmenorrhea in women scheduled for laparoscopic treatment of possible endometriosis: a double blind randomised controlled trial

Protocol Number: 1 Version 0.5, dated 29 September 2020

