In another study on rats with induced endometriosis, markers such as MCs, chymase, NGF, VEGF, and Flk1 (VEGF receptor) were shown to be significantly reduced under PEA/PLD treatment. More importantly, treatment resulted in fewer episodes of uterine pain and smaller endometriotic cysts size (42). Pain was assessed by recognizing characteristic positional behavior known to be associated with uterine pain. These results in rats suggest that PEA/PLD may act both by reducing pain and by reducing lesion size and/or activity.

Study Name: Palmitoylethanolamide and polydatin effect on pain and dysmenorrhea in women scheduled for laparoscopic treatment of possible endometriosis: a double blind randomised controlled trial

Protocol Number: 1 Version 0.5, dated 29 September 2020

The aim of this study is to assess the efficacy of PEA/PLD for pain reduction in patients with endometriosis, and to investigate the effect of PEA/PLD on lesion cellular and molecular markers including MC, chymase, NGF, VEGF, and Flk1 (VEGF receptor) expression.

This study looks at the analgesic and anti-inflammatory effects of PEA/PLD on endometriosis related pain prior to and following surgical treatment. We aim to look at the difference in inflammatory markers in the endometriotic lesions, as well as in peritoneal biopsies and fluid between PEA/PLD and placebo.

4. Study Objectives

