4.1. Hypotheses

- 4.1.1. There will be no change in VAS scores for dysmenorrhoea, dyspareunia, dyschezia and persistent pelvic pain between baseline pain and after 8 weeks of treatment with PEA/PLD versus placebo.
- 4.1.2. There will be no difference in VAS scores for dysmenorrhoea, dyspareunia, dyschezia and persistent pelvic pain after 8 weeks of treatment between patients treated by PEA/PLD compared with placebo.
- 4.1.3. There will be no difference in VAS scores for dysmenorrhoea, dyspareunia, dyschezia and persistent pelvic pain between patients treated by PEA/PLD compared with placebo, 4 months' after surgery.
- 4.1.4. There will be no change in cellular and molecular markers in endometriotic lesions, blood and peritoneal fluid in patients treated by PEA/PLD compared with placebo.

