4.3. Outcome Measures

Primary outcomes

- 4.3.1. To compare the change in dysmenorrhoea VAS score between PEA/PLD and placebo treatment in patients with endometriosis prior to laparoscopic surgical treatment.
- 4.3.2. To compare the change in dyspareunia, dyschezia and persistent pelvic pain VAS score between PEA/PLD and placebo treatment in patients with endometriosis prior to laparoscopic surgical treatment.

Secondary outcomes

- 4.3.3. To compare the change in dysmenorrhoea VAS score between PEA/PLD and placebo treatment at baseline and 4 months after laparoscopic surgery for endometriosis.
- 4.3.4. To compare the change in dyspareunia, dyschezia and persistent pelvic pain VAS score between PEA/PLD and placebo treatment at baseline and 4 months after laparoscopic surgery for endometriosis.

Study Name: Palmitoylethanolamide and polydatin effect on pain and dysmenorrhea in women scheduled for laparoscopic treatment of possible endometriosis: a double blind randomised controlled trial

Protocol Number: 1 Version 0.5, dated 29 September 2020

- 4.3.5. To compare the change in dysmenorrhoea, dyspareunia, dyschezia and persistent pelvic pain VAS score between PEA/PLD and placebo, before surgery, in patients without surgical evidence of endometriosis.
- 4.3.6. To compare the change in dysmenorrhoea, dyspareunia, dyschezia and persistent pelvic pain VAS score between PEA/PLD and placebo, at baseline and 4 months after laparoscopic surgery without evidence of endometriosis.
- 4.3.7. To compare the change of quality of life between PEA/PLD and placebo treatment in women with surgical evidence of endometriosis, before surgery and again after surgery.
- 4.3.8. To compare changes in cellular and molecular markers from endometriotic lesions, blood and peritoneal fluid samples between patients treated by PEA/PLD and placebo.
- 4.3.9. To correlate changes in VAS score with changes in cellular and molecular markers, in patients with endometriosis, treated by PEA/PLD and placebo.
- 4.3.10. To assess the side effects of PEA/PLD.

5. Study Design

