Endometriotic lesions/cysts and peritoneal tissue: Two small samples of endometriotic lesion tissue will be taken by scissors (not diathermy) as fresh tissue and 1) stored in RNALater for RNA extraction (NGS analysis) and 2) stored in tissue media on ice for immediate in vitro cell culture studies. The formalin fixed lesions sample(s) collected as part of the routine histopathology process and diagnosis, will be accessed for research following routine histopathology assessment.

All other endometriosis lesions will be excised routinely by monopolar diathermy and submitted for routine histopathology. Paraffin embedded ectopic endometrium or peritoneum will only be recalled from pathology following completion of histopathological review (i.e. excess to pathology diagnostic requirements).

Peritoneal Fluid: a sample of peritoneal fluid (up to 10 ml) will be removed for research purposes and frozen for later use. If peritoneal fluid is not found, a saline light wash of

Study Name: Palmitoylethanolamide and polydatin effect on pain and dysmenorrhea in women scheduled for laparoscopic treatment of possible endometriosis: a double blind randomised controlled trial

Protocol Number: 1 Version 0.5, dated 29 September 2020

the pelvis will be done. This does not pose any additional risk for the patient except for extending surgical time by another 1-2 minutes. Samples will be stored at -80°C.

If no active endometriosis is seen, a small biopsy for histological assessment, immunohistochemistry and RNA analysis will be taken by scissors from one of the utero-sacral ligaments.

Surgeons will complete a dedicated operation report on surgical findings immediately after surgery, staging the endometriosis based on the revised American Society for Reproductive Medicine classification of endometriosis (rASRM).

Surgery and post-operative care will otherwise be unaffected by participation in the study. All surgeons and study investigators will be blinded to the patient's allocation to treatment or placebo groups.

Patients will be asked to complete a repeat questionnaire at 4 months' time after surgery.

Tissue bank samples: Endometriotic lesions and endometrium will be stored in RNALater for molecular analysis and/or formalin fixed for routine pathology. Tissues will be stored in the research precinct or recalled from pathology.

Menstrual cycle stage will be determined by pathology.

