8.1. Sample Size Estimation & Justification

The sample size required for a one point difference on the numerical pain scale between PEA/PLD treatment and placebo in the change of each type of pain measured VAS score before (at recruitment) and at 4 months after surgery, and SD of 2 (based on a previous study performed by our team), was calculated to be 128 (64 in each group), based on an alpha of 0.05, power of 0.8 and two sided p-value. Allowing for a drop-out rate of 30%, and assuming that 30% of patients will not be found to have endometriosis on surgery, a total sample size required is 130 in each group (N=260).

If the participant withdraws prior to completing 6 weeks of medical treatment, she will be removed from the study.

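### The protocol's only significance rule, p<0.05, applies unchanged to a family of at least five markers under one null hypothesis, so the error rate for the marker question is well above 5%

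*Protocol*

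**What the plan says.** The synopsis (Statistical Methods) lists t-tests, Mann-Whitney, chi-squared and Fisher tests and then says "P values of <0.05 will be considered significant". Section 8.2 repeats the tests without a threshold or any adjustment. The only other mention of alpha is in the sample size (section 8.1): "based on an alpha of 0.05, power of 0.8 and two sided p-value".

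The marker work appears in several places:

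- The study question in the synopsis asks "what are the cellular and molecular mechanisms modified by PEA/PLD treatment in endometriotic lesions".
- The aim at the end of section 3.2 covers "lesion cellular and molecular markers including MC, chymase, NGF, VEGF, and Flk1 (VEGF receptor) expression". That is five named markers, in an open list.
- Section 4.1.4 gives the marker work its own null: "There will be no change in cellular and molecular markers in endometriotic lesions, blood and peritoneal fluid".
- Section 4.3.8 makes the between-arm marker comparison in these three specimen types a secondary outcome. Section 4.3.9 adds another: "To correlate changes in VAS score with changes in cellular and molecular markers, in patients with endometriosis, treated by PEA/PLD and placebo".
- Section 5.4 sends lesion and endometrial RNA for sequencing but describes no analysis of it.

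No section names a lead marker, says which markers are measured in which specimen, or calls this work exploratory.

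**The concern.** Hypothesis 4.1.4 is written as one null but can only be tested through several comparisons. The protocol does not say how many of them, or which, must be significant before the null is rejected. Read with the synopsis rule, any single marker below 0.05 would count as a significant finding. The probability of rejecting 4.1.4 wrongly then grows with the number of markers and specimens.

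The mechanism is half of the study question, so a false rejection matters. An isolated marker result could be reported as a mechanism of action for a product that changed none of the markers. The correlations in 4.3.9 face the same problem, with each marker set against four pain scores. Any correction applied to the primary pain scores would leave these families untouched.

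**Working it through.** **The plan's own figure.** The protocol states no family-wise error rate. Its one calculation that uses alpha is the sample size. "The sample size required for a one point difference on the numerical pain scale" is set with SD 2, power 0.8 and two-sided alpha 0.05. The normal approximation gives 2 × (1.960 + 0.842)² × 2² / 1² = 62.8, so 63 per arm. The t-test solution is 63.8, so 64 per arm and 128 in total, as stated. Inflating for 30% drop-out and 30% without endometriosis gives 64 / (0.7 × 0.7) = 130.6, against 130 stated. The figure reproduces. It concerns a single pain comparison and has no bearing on the markers.

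**Inputs for the marker family.**

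- Threshold per test: two-sided 0.05 (synopsis; sidedness from section 8.1).
- Named markers: 5 (section 3.2: MC, chymase, NGF, VEGF, Flk1).
- Specimen types: 3 (sections 4.1.4 and 4.3.8). That all five markers are measured in all three is an assumption; section 3.2 ties the five to lesions.
- Correlation between test statistics: not given. It is assumed equal for all pairs and ranged from 0 to 0.8, with 0.5 as the central value.

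**Formula.** For k independent tests with no true effect, P(at least one p<0.05) = 1 − 0.95^k.

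- k = 5: 1 − 0.774 = 22.6%.
- k = 15 (5 × 3): 1 − 0.463 = 53.7%.

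For correlated tests the same probability was obtained for equicorrelated normal statistics with two-sided limits of ±1.96.

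| Tests | Correlation 0 | 0.5 | 0.7 | 0.8 |
|---|---|---|---|---|
| 5 (lesions only) | 22.6% | 18.3% | 14.8% | 12.7% |
| 15 (5 markers × 3 specimens, assumed) | 53.7% | 36.1% | 25.7% | 20.2% |

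The smallest entry, 12.7%, is about 2.5 times the nominal 5%. The expected number of false positives is 5 × 0.05 = 0.25 for lesions only and 15 × 0.05 = 0.75 for the assumed 15 tests, whatever the correlation.

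**Scale of a correction.** As a benchmark, Bonferroni would test at 0.05/5 = 0.010 for five tests or 0.05/15 = 0.0033 for fifteen. Under independence the family-wise error is then about 4.9% in both cases.

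**What near-certainty would need.** Reaching 95% takes ln(0.05)/ln(0.95) = 58.4, so about 59 independent tests. The named markers do not come to that number.

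**The case against.** The strongest objection is that multiplicity for secondary laboratory outcomes is normally settled in a statistical analysis plan, which may exist and is not shown. The protocol does not say that the marker tests will go unadjusted. The threshold is a conventional synopsis line, placed after the categorical tests, and section 8.2 does not repeat it. The study aim in section 4.2 is pain only, both primary outcomes are pain scores, and the markers come late among the secondary outcomes.

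Part of this stands. The protocol does rank the markers below pain, and nothing in it says that a marker result could establish efficacy. But the protocol is not merely silent. It states a rule without limits and a formal null that the rule would decide. A later plan that controlled the error rate would have to narrow the protocol's own sentence.

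A reader might also infer three stronger points that the document does not support:

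- **A false positive is almost certain.** For the named markers, no false positive is the likelier result in every case calculated except 15 fully independent tests.
- **Sequencing will produce hundreds of false genes.** Sequencing appears only in the sample-handling text. No section describes gene-by-gene testing at 0.05 or gives a number of genes. Endometrial RNA also lies outside 4.1.4, which covers lesions, blood and peritoneal fluid.
- **The clinical secondary outcomes 4.3.3 to 4.3.7 should be demoted or gated on the primary.** The protocol lists four primary pain scores, so the gate would be undefined. Section 8.1 also sizes the trial on the pain change to 4 months after surgery, which belongs to 4.3.3 and 4.3.4. Demoting those outcomes is a trade-off that this point does not settle.

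**Conclusion.** The point holds for the marker family. Under the only decision rule stated, the chance of wrongly finding at least one significant marker when there is no effect is about 18% for five lesion markers (13% to 23%). It is about 36% (20% to 54%) if all five are tested in all three specimens. The ranges cover correlations from 0.8 down to 0. They assume two-sided tests, equal correlation and no true effect on any marker. The 15-test figure also rests on a marker-by-specimen layout that the protocol does not fix. The marker list is open, so five is a minimum for lesions. The pain comparisons and the sample size are not affected. This is a correction the sponsor should make, best settled before unblinding, because a lead marker chosen afterwards would not be credible.

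**What to change.** Reword the synopsis sentence so that the unadjusted 0.05 threshold does not apply test by test to 4.3.8 and 4.3.9, and carry the limit into section 8.2. Then:

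- Analyse the marker-by-specimen comparisons (4.3.8) and the marker-pain correlations (4.3.9) as two families, each with Benjamini-Hochberg false-discovery control, for example at 5%. Alternatively, name one lead lesion marker in advance as the single test of 4.1.4 and apply false-discovery control to the rest.
- Treat any sequencing comparison in the same way, as its own family.
- Label these marker, correlation and sequencing results exploratory.

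This changes wording in the protocol or analysis plan and needs no extra patients or samples. The cost is that fewer individual markers can be called significant.

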1. GLOSSARY OF ABBREVIATIONS & TERMS

Abbreviation	Description (using lay language)
PEA	Palmitoylethanolamide
PLD	Polydatin
NSAID's	Non-Steroidal Anti-Inflammatory drugs
MCs	Mast cells
VAS	visual analog scale
PPP	Persistent pelvic pain
NGF	Nerve growth factor
VEGF	Vascular endothelial growth factor
Flk1	Fetal Liver Kinase 1
NECST	The National Endometriosis Clinical and Scientific Trials
REDCap	Research Electronic Data Capture
RAFS	Revised American Fertility Society

Study Name: Palmitoylethanolamide and polydatin effect on pain and dysmenorrhea in women scheduled for laparoscopic treatment of possible endometriosis: a double blind randomised controlled trial

Protocol Number: 1 Version 0.5, dated 29 September 2020

2. Study Sites

3.1. Lay Summary

Effective medical therapies for the treatment of endometriosis related pelvic pain are limited and are often associated with side-effects.

Palmitoylethanolamide (PEA) is a food supplement that has been shown to have anti-inflammatory action.

Polydatin (PLD) is also a food supplement that has antioxidant and pain inhibiting activities.

There have been some small studies performed to assess if the combination of PEA/PLD is helpful for persistent pain associated with endometriosis. The results suggest it might have benefit, but further studies are required.

Multiple studies that assessed PEA/PLD for pain relief in various other pain conditions have not reported any significant side effects.

The aim of this study is to determine if treatment with PEA/PLD improves endometriosis associated pain.

Women who are booked for surgical treatment of possible endometriosis will be offered participation in this study. Participation will not change their surgeon's care plan. The participants will be randomised to either receive 8 weeks of PEA/PLD treatment or placebo prior to their surgery. The endometriosis will then be confirmed or excluded during the surgery. Lesions of endometriosis, endometrium, pelvic fluid and blood will be collected where possible to assess inflammatory markers.

Participants will also complete a survey including pain and quality of life assessments. This survey will be completed at recruitment, after 8 weeks of treatment (pre surgery) and at 6 months (4 months after surgery).

We will assess the change in pain scores and quality of life scores between the 2 groups to see if PEA/PLD is beneficial.

3.2. Background information

Study Name: Palmitoylethanolamide and polydatin effect on pain and dysmenorrhea in women scheduled for laparoscopic treatment of possible endometriosis: a double blind randomised controlled trial

Protocol Number: 1 Version 0.5, dated 29 September 2020

This study is one of nine projects being run as part of a program of endometriosis research recently funded by MRFF (MRF9911715 'Improving diagnosis and treatment of endometriosis' \$3.94 million over 5 years). The program is being run through the University of Melbourne Department of Obstetrics and Gynaecology and contains a mixture of clinical trials and laboratory-based studies. Subjects will be recruited for the research program from the Departments' teaching hospitals (primary sites are RWH and Mercy) as well as from listed hospitals where clinicians who are part of each project undertake public and private sessions.

Core datasets for all subjects will be collected using the National Endometriosis Clinical and Scientific Trials (NECST) Network Registry. The NECST Registry is a MRFF funded initiative to create a nationally co-ordinated database containing securely held patient details, clinical history, diagnostic results, treatment details and health outcomes, for patients who have given informed consent for their details to be included, to support research into endometriosis. This national database will underpin a comprehensive national program of clinical, basic science and translational research relevant to the needs of Australians with endometriosis, consistent with the research objectives in the National Action Plan for Endometriosis. The NECST Registry is currently in final stages of developmental testing and has conditional HREC approval from Monash Health (Study Title: Establishment of the National Endometriosis Clinical and Scientific Trials (NECST) Network Registry. ERM Reference Number: 62508. Monash Health Reference: RES-20-0000-258A). The project was reviewed by the Monash Health Human Research Ethics Committee at its meeting on 07 May 2020 and was approved subject to conditions. The responses are to be reviewed outside of the Committee by the Medical Administrator and Research Support Services staff. We will not commence recruitment for our program of research until the Monash HREC approval for NECST is finalised and Site-Specific Approvals have been obtained from our participating hospitals

Subjects recruited to projects in our program will need to be consented for both NECST and the specific project(s) they are taking part in. We are not seeking HREC approval for patients to enter data into NECST as that will fall under the Monash approval. However, as part of the current HREC application we require approval to access the relevant core data for each of our subjects collected in NECST for our research program. This will allow us to use NECST as a facility to collect core data that supports our program as well as contributes to growing the National Endometriosis Registry.

In addition to the NECST core dataset, we will collect project-specific data for each of our projects. Project-specific data may be relevant to 1 or more of our projects. To assist evaluation of our projects by the Austin HREC, we have compiled a full list of all the NECST and project specific questions that we will use, accompanied by a 'road map' indicating which questions this project (and all of our other projects) will ask of its participants. Participants will only complete questions for the project(s) that they have consented to participate in.

Paperwork and data from this project will be kept in a locked room at The Royal Women's and Mercy Hospitals. All computerized information will be kept in a

Study Name: Palmitoylethanolamide and polydatin effect on pain and dysmenorrhea in women scheduled for laparoscopic treatment of possible endometriosis: a double blind randomised controlled trial

Protocol Number: 1 Version 0.5, dated 29 September 2020

database that is password protected. Only researchers named on this project will have access. All project-specific information will be kept for a period of 7 years after the project is completed, at which time hard copy records will be shredded and computer files deleted.

Endometriosis is a common condition with recent data estimating an 11.4% lifetime risk in women of reproductive age in Australia. Symptoms include chronic pelvic pain, infertility and fatigue (1). It is an oestrogen-dependent inflammatory disease, but its etiology and pathophysiology are unclear. Frontline treatments for endometriosis include one or more of surgery, medications containing hormones and analgesia; primarily with NSAID's. Pain control with these options is often limited and associated with a relatively high rate of side effects (2).

Inflammation has been shown to have a major role in endometriosis (3).

Inflammatory processes are regulated by mast cells (MCs) (4, 5, 6) which are found close to nerve fibers in endometriotic lesions (7, 8) and play a role in several normal female processes including reproduction, pregnancy, and labour (9). It has been suggested that endometrial MC function

may be altered by the local steroid microenvironment (10). Increased numbers of activated mast cells have been found in endometriotic lesions, particularly in deep infiltrating lesions proximal to nerves, suggesting that MCs may contribute to endometriosis pain by a direct effect on nerve function (11,12). Conceivably, MC activation during inflammation may contribute to pain development and hyperalgesia in endometriotic lesions (13, 14, 15). MC targeted treatment could thus prove useful for pain relief in endometriosis (16).

Palmitoylethanolamide (PEA) is a member of the N-acylethanolamine family of fatty acid amides. It is a signaling molecule which down-regulates MC activation and microglial cell function (17, 18, 19). It is a structural analog of anandamide an endogenous ligand for cannabinoid receptors CB1 and CB2 that has been reported to show a variety of cannabimimetic activities with anti-inflammatory, immunosuppressive, analgesic, neuroprotective, and antioxidant effects (20).

Recently, PEA has been proposed to enhance the activity and/or inhibit the degradation of endogenous agonists of cannabinoid receptors. This would lead to a reinforcement of their actions at the level of several possible targets, which include the heat-activated transient receptor potential vanilloid type 1 (TRPV1) channels, the receptors for capsaicin; in addition, PEA activates the peroxisome proliferator-activated receptor- α (PPAR α) transcription factor, thereby suggesting PPAR α as a relevant molecular target for at least some of PEA's actions. An activation of PPAR α and TRPV1 channels has been demonstrated in the pathogenesis of pain in sensory neurons. Therefore, treatment with PEA, by promoting a higher degree of TRPV1 desensitization, might be associated with a good analgesic effect and a lower incidence of adverse events (21).

Transpolydatin (PLD) is a precursor of resveratrol, a phytoalexin polyphenolic compound found in a variety of plants, such as grapes, berries, and peanuts, that downregulates the inflammatory response through inhibition of synthesis and release of proinflammatory mediators and MCs degranulation and modifies eicosanoid synthesis (22). In experimental models of endometriosis, Resveratrol has been shown

Study Name: Palmitoylethanolamide and polydatin effect on pain and dysmenorrhea in women scheduled for laparoscopic treatment of possible endometriosis: a double blind randomised controlled trial

Protocol Number: 1 Version 0.5, dated 29 September 2020

to bring about regression of endometriotic lesions (23). This is likely to be related to its strong anti-angiogenic and anti-inflammatory actions (24). Polydatin (PLD) is a molecule with documented antioxidant and anti-chemotactic activities. It has been given in combination with PEA in at least 2 studies for the treatment of endometriosis associated pain (25, 26), and in other studies assessing pain control of other chronic pain conditions.

A meta-analysis published in 2017, summarized all observational and RCTs treating endometriosis associated persistent pelvic pain (PPP) with the combination of PEA/PLD up to 19 July 2015 (27). Inclusion criteria were VAS/VAS like assessment before and after treatment. Out of 13 studies, only 4 were included in the final analysis (26, 28, 29, 30). Their conclusion was that the administration of micronized PEA/trans-PLD (400 mg/40 mg) twice a day for three months provided a clinically relevant improvement of chronic pelvic pain and dysmenorrhea while improving deep dyspareunia to a limited degree. No clinically relevant improvement was found for dyschezia. The total number of patients treated by PEA/PLD in all four studies was 82. Only one study (28) was a randomized double-blind study. Another study (30) was randomized open-label and the other 2 were observational.

Since July 2015, only two more studies investigating treatment of endometriosis with PEA have been published: Caruso et al (31) showed that a combination of 300 mg PEA and 300 mg alpha-lipoic acid, reduced pain in 56 patients with endometriosis after 6 months.

De Leo V et al (32) published a multi-centre study of 60 women treated by a combination of alpha-lipoic acid (a powerful natural antioxidant and enzymatic cofactor of the mitochondrial respiratory chain), PEA and myrrh (an aromatic gum-resin extracted from a tree or shrub of the genus *Commiphora* that has antibacterial, antifungal and anaesthetic properties). They showed a significant reduction in pain symptoms including dyspareunia, dysmenorrhea and chronic pelvic pain, with no change in the mean diameter of endometriomas.

Previous studies comparing PEA/PLD treatment with placebo in endometriosis included no more than 20 patients in each arm and were of poor quality (28).

A large study testing the effect of PEA/PLD compared to placebo on primary dysmenorrhoea, included 110 patients in each arm (220 patients in total). An improvement of pelvic pain was seen in 98.18% (95% confidence interval 97.64% to 98.60%) of cases in the PEA/PLD group vs 56.36% (95% confidence interval 48.62% to 63.81%) in the placebo group ($P < .001$). The combination of PEA/PLD was more effective than placebo ($P < .001$). Treatment was given for 10 days, from day 24 of the cycle (33).

A meta-analysis summarizing all double blind RCT of different inflammatory chronic pain conditions treated by PEA versus placebo or other analgesia, was published in 2017 (34). 10 studies looking into sciatic pain, chronic pelvic pain, temporomandibular joint arthritis, vestibulodynia, carpal tunnel syndrome, and molar surgery were included. 786 patients received PEA. PEA was associated with significantly greater pain reduction compared to inactive control conditions ($P <$

Study Name: Palmitoylethanolamide and polydatin effect on pain and dysmenorrhea in women scheduled for laparoscopic treatment of possible endometriosis: a double blind randomised controlled trial

Protocol Number: 1 Version 0.5, dated 29 September 2020

0.001). Use of placebo control, presence of blinding, allowance for concomitant treatments, and duration or dose of PEA treatment did not affect the measured efficacy of PEA.

Both PEA and polydatin are food supplements that are been sold over the counter and are widely in use for treatment of varied conditions.

The tolerability of the PEA was reviewed in the above meta-analysis (34). Adverse events reported from PEA treatment to 786 patients included only gastrointestinal upset (2), drowsiness (1), and heart palpitations (1). No significant adverse side effects were reported in other studies. Moreover, treatment was given to patients seeking fertility, after surgical diagnosis of endometriosis while trying to conceive with no concern of teratogenicity (35).

Worldwide, more than 800,000 patients have been treated with PEA, most of them in Italy and Spain, with some in The Netherlands, Germany, UK, Canada and the US, and no serious side effects that have been reported (36).

Polydatin or its origin Reserveol, are widely used in humans because of their reported potential antitumor and anti-inflammatory properties (37). Despite the extensive research on the benefits derived from Reserveol, there was not enough research conducted to assess its harmful effects. In high doses of Reserveol (2-5 g per day) can lead to episodes of light and mild diarrhea, nausea, hypersensitivity and anal pruritus.

It appears that Reserveol needs to be administered in extremely high doses for it to elicit a significant toxic effect in vivo. It is generally well tolerated, some adverse effects including nephrotoxicity and gastrointestinal problems were reported in human subjects taking high dose (more than 1000 mg/day) (38, 39). A 450 mg/day dose of Reserveol was reported to be a safe dose for a 60-kg person (40). Overall, Reserveol is well tolerated in healthy individuals.

Interestingly, Di Paola R. et al, (41) suggested that PEA/PLD may be of use to inhibit development of endometriotic lesions in rats. In the treated group (N=10), a smaller endometriosis lesion diameter was found (as compared to controls), with improved fibrosis score and mast cell number decrease. PEA/PLD administration also decreased angiogenesis (vascular endothelial growth factor), nerve growth factor, intercellular adhesion molecule, matrix metalloproteinase 9 expression, and lymphocyte accumulation. It also reduced peroxynitrite formation, (poly-ADP) ribose polymerase activation, I κ B alpha phosphorylation and nuclear factor- κ B translocation to the nucleus.

In another study on rats with induced endometriosis, markers such as MCs, chymase, NGF, VEGF, and Flk1 (VEGF receptor) were shown to be significantly reduced under PEA/PLD treatment. More importantly, treatment resulted in fewer episodes of uterine pain and smaller endometriotic cysts size (42). Pain was assessed by recognizing characteristic positional behavior known to be associated with uterine pain. These results in rats suggest that PEA/PLD may act both by reducing pain and by reducing lesion size and/or activity.

Study Name: Palmitoylethanolamide and polydatin effect on pain and dysmenorrhea in women scheduled for laparoscopic treatment of possible endometriosis: a double blind randomised controlled trial

Protocol Number: 1 Version 0.5, dated 29 September 2020

The aim of this study is to assess the efficacy of PEA/PLD for pain reduction in patients with endometriosis, and to investigate the effect of PEA/PLD on lesion cellular and molecular markers including MC, chymase, NGF, VEGF, and Flk1 (VEGF receptor) expression.

This study looks at the analgesic and anti-inflammatory effects of PEA/PLD on endometriosis related pain prior to and following surgical treatment. We aim to look at the difference in inflammatory markers in the endometriotic lesions, as well as in peritoneal biopsies and fluid between PEA/PLD and placebo.

4. Study Objectives

